7.1.1.4. Blood draw for laboratory panel at 5-9 days and 12-16 days post-bronchoscopy

7.1.1.5. Only experienced pathology attendings will make the ROSE determination during the procedure (e.g. fellows will not perform the ROSE diagnosis)

7.1.2. Criteria under which an INDIVIDUAL SUBJECT'S study treatment or study participation would be stopped or modified:

7.1.2.1. At subject, PI, or study team member request

7.1.2.2. If the subject had a Serious Adverse Event (SAE) deemed related to study  
Other: specify

7.1.2.3. During the bronchoscopy, bleeding >100mL or concern for a patient's ability to continue to tolerate the bronchoscopy would result in stopping that procedure (regardless of whether cisplatin had been delivered into the tumor or not). No further intratumoral delivery would be performed.

7.1.3. Criteria under which THE ENTIRE STUDY would need to be stopped.

7.1.3.1. A 30% or greater rate of possibly related, serious, unanticipated events after 6 patients, will trigger halting of the study and initiate IRB and DSMCC review.

7.1.4. Withdrawals/dropout reporting to the IRB prior to study completion will occur at the IRB annual continuing renewal submission

7.1.5. Plan for management of incidental findings:

7.1.5.1. We do not anticipate incidental findings. The pre-bronchoscopy CT scan is obtained as part of clinical care for all patients undergoing a clinically indicated bronchoscopy. Unanticipated findings on the pre-resection CT will be evaluated as potential AEs.

## 7.2. Adverse Events:

7.2.1. Definition of adverse events (AE) for this study:

7.2.1.1. An adverse event (AE) will be considered any undesirable sign, symptom or medical or psychological condition even if the event is not considered to be related to the investigational drug/device/intervention. Medical conditions/diseases present before starting the investigational drug/intervention will be considered AEs only if they worsen after starting study treatment/intervention. An AE is also any undesirable and unintended effect of research occurring in human subjects as a result of the collection of identifiable

private information under the research. AEs also include any problems associated with the use of an investigational device that adversely affects the rights, safety or welfare of subjects.

7.2.2. Define of serious adverse events (SAEs):

7.2.2.1. A serious adverse event (SAE) will be considered any undesirable sign, symptom, or medical condition which is fatal, life-threatening, requires or prolongs inpatient hospitalization, results in persistent or significant disability/incapacity, constitutes a congenital anomaly/ birth defect, is medically significant and which the investigator regards as serious based on appropriate medical judgment. An important medical event is any AE that may not result in death, be life-threatening, or require hospitalization but may be considered an SAE when, based upon appropriate medical judgment, it may jeopardize the patient and may require medical or surgical intervention to prevent one of the outcomes listed in the definitions of SAEs.

7.2.2.2. Any serious psychological and emotional distress resulting from study participation (suggesting need for professional counseling or intervention).

7.2.3. ALL AEs above will be collected/ recorded.

7.2.4. A REDCap database will be used to save and manage data.

7.2.4.1. The database is located on the secure UVM server and is firewall protected. Data will be collected from source documents including but not limited to clinic notes, laboratory results, and other EMR available documents. The PI will review all AE data at the end of the study period for each patient. Data will be entered and managed by trained study personnel.

7.2.5. AEs be classified/graded using NCI Common Toxicity Criteria for Adverse Events (CTCAE), Version 5.0

7.2.6. The PI will determine the relationship of AEs to the study using the following scale:

7.2.6.1. Definite: AE is clearly related in time and a direct association can be demonstrated to the study intervention.

7.2.6.2. Probable: AE is reasonably related in time and is more likely explained by the study intervention than by other causes.

7.2.6.3. Possible: AE may be reasonably related in time and the AE can be explained equally well by causes other than the study intervention.

7.2.6.4. Unlikely: A potential relationship could exist with the study intervention, but the AE is most likely explained by other causes.

7.2.6.5. Unrelated:AE is clearly not related to intervention and can be fully explained by another cause. This other cause should be provided.

7.2.7. Recording/reporting of baseline AEs will begin after the subject signs consent. Subsequent AEs will be recorded following initiation of the bronchoscopic procedure.

7.2.8. Recording/reporting of AEs will end following surgical resection or 30 days after cisplatin delivery, whichever occurs first.

7.2.9. The PI will review all AEs following the 1 week follow up visit (occurs at 5-9 days performed by a physician or advanced practice provider), both to assess for unexpected and serious AEs and to ensure that dose escalation occurs consistent with the statistical plan.

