3.1.3.1. Leukocytes  $\geq$ 3,000/mcL

3.1.3.2. Platelets  $\geq$ 100,000/mcL

3.1.3.3. Total bilirubin  $\leq$  institutional upper limit of normal (ULN)

3.1.3.4. AST(SGOT)/ALT(SGPT)  $\leq$ 3  $\times$  institutional ULN

**Figure 1: Dosing of Cisplatin Based on Tumor Volume.** Isodose lines demonstrate robust coverage of small tumors with low doses of intratumoral cisplatin (1mg/ml). For reference, a 10 cm^3 volume corresponds to a 2.7 cm diameter tumor (assuming a spherical morphology).

- 3.1.3.5. Creatinine  $\leq$  institutional ULN
- 3.1.4. Patients with a prior or concurrent malignancy whose natural history or treatment does not have the potential to interfere with the safety or efficacy assessment of the investigational regimen are eligible for this trial
- 3.1.5. Have known or suspected clinical stage I-IIb NSCLC after CT and/or PET\_CT at time of enrollment
- 3.1.6. Presence of a target lesion with a minimum volume of 1.0 cm^3, (approximately 1.2 cm in diameter) and  $\leq$  5.0 cm in diameter
- 3.1.7. Agreement from a cardiothoracic surgeon, following review of past medical history, medications, pulmonary function testing, and CT scan that patient is likely to be a surgical candidate and that, after considering known possible adverse events, delivery of intratumoral cisplatin is unlikely to adversely affect surgical feasibility
- 3.1.8. Rapid on-site cytopathologic examination (ROSE) performed during the procedure returns likely NSCLC (per the determination of a trained, attending, cytopathologist). No research procedures will be performed if ROSE is non-diagnostic
- 3.1.9. A CT scan of the chest (with or without contrast) within 1 month of the screening visit
- 3.1.10. Ability to understand and the willingness to sign a written informed consent document

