#### 4.2. Duration of Study Period:

4.2.1. There is only a single delivery of the agent, cisplatin.

4.2.2. Primary endpoint adjudication for DLT will occur after the 2 week post-procedure evaluation and laboratory values are completed.

4.2.3. The patient will be monitored for adverse events until surgical resection or for 30 days after cisplatin delivery, whichever occurs first.

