4.3.4.3. Blood will be drawn for an additional platinum level.(research)

**4.3.5. 2 Week Post-Bronchoscopy Follow Up**

4.3.5.1. Participants will undergo an evaluation by a physician or advanced practice provider between 12-16 days post-procedure. Visit will occur in-person. The only exception would be COVID related issues. In that case, telemedicine and local labs will be allowed. No phone evaluations will occur unless there is no other option. A standard script will be used to assess for AEs. (research)

4.3.5.2. A blood draw to assess for AEs will be performed between 12-16 days post-procedure.(research)

4.3.5.2.1. Samples for the following laboratory tests will be sent to UVMMC laboratories for analysis:

- 4.3.5.2.1.1. Hematology Panel
- 4.3.5.2.1.2. Chemistry Panel
- 4.3.5.2.1.3. Liver Panel

4.3.6. A Chest CT will be performed between 12 and 30 days after delivery of the cisplatin.(research)

4.3.7. Surgical Resection, if planned, will be scheduled between 14 and 30 days after delivery of the cisplatin.

4.3.7.1. Approximately 15mL of blood will be drawn for research purposes on the day of (prior to) the resection procedure.

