8.1.1.1.3. Suggests that the research places subjects or others at a greater risk

of harm (including physical, psychological, economic, or social harm) related to the research than was previously known or recognized.

8.1.1.2. Definition of a protocol deviation:

8.1.1.2.1. A protocol deviation is any variance from the protocol involving a subject or subjects that is not approved by the IRB prior to its initiation or implementation, and occurs when a member of the study team departs from the IRB-approved protocol in any way without the investigator first obtaining IRB approval

8.1.1.3. Recording/reporting of Unanticipated Problems and Protocol Deviations will begin after the subject signs consent

8.1.1.4. Recording/reporting of Unanticipated Problems and Protocol Deviations will end at surgical resection or 30 days after cisplatin delivery, whichever occurs first.

8.1.2. Unanticipated Problem, and Protocol Deviation reporting.

Type of Event	To whom will it be reported	Time Frame for Reporting	How to report?
Unanticipated Problems that are not AEs or protocol deviations.	IRB and DSMC	Within 7 days to both the IRB and DSMC	DSMC: Email IRB: Click form

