9.8. This aggregate review will occur quarterly

**1. TABLE OF STUDY VISITS AND PROCEDURES:**

	Screening	Phase 1: Intratumoral Cisplatin Protocol					
		Pre-Bronchoscopy	Bronchoscopic Procedure	24H Followup	1 Week Followup	2 Week Followup	Surgical Resection**
Study Visit							
Informed Consent	X						
History and Evaluation	X			X	X	X	
Research Biopsies			X				
Delivery of Cisplatin			X				
Cisplatin Blood Levels			X	X	X		
CXR	X (pre-bronchoscopy if no imaging within prior 7 days)		X (post-procedure)				
24H Post-Procedure Follow Up				X			
Hematology Panel	X				X	X	
Chemistry Panel	X				X	X	
Liver Panel	X				X	X	
Albumin	X						
Blood Draw for Research			X				X (day of resection)
Review of Adverse Events and Concomitant Medications				X	X	X	
Chest CT Scan (non-contrast if not performed or inadequate will be ordered for research purposes)	X					X	
Obtain Research Resected Pathology Specimen							X (fresh and fixed)

\* Research biopsies will be evaluated for changes in immunocellular infiltrate vs. resection specimen

\*\*Surgical resection to occur 14-30 days post-procedure

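### Safety recording closes at resection, so this pre-operative injection has no post-operative adverse-event data, and the plan is ambiguous about intra-operative events

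*Combined protocol and SAP*

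**What the plan says.** Three sections of the combined protocol and SAP set the end of safety recording.

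- Section 7.2.8: "Recording/reporting of AEs will end following surgical resection or 30 days after cisplatin delivery, whichever occurs first".
- Section 4.2.3: "The patient will be monitored for adverse events until surgical resection or for 30 days after cisplatin delivery, whichever occurs first".
- Section 8.1.1.4, for unanticipated problems and deviations: recording "will end at surgical resection or 30 days after cisplatin delivery, whichever occurs first".

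On the timing of surgery, section 4.3.7 says: "Surgical Resection, if planned, will be scheduled between 14 and 30 days after delivery of the cisplatin". The footnote to the table of study visits agrees: "Surgical resection to occur 14-30 days post-procedure". Resection is the last column of that table. It has marks for a research blood draw and specimen collection, and none for adverse-event review.

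The surgery-related outcomes are the proportion reaching surgery without extended injection-related delay (6.2.2.2) and time to surgery (6.2.2.3). Section 7.1 also makes a delay in resection a reportable adverse event. Eligibility (3.1.7) requires a surgeon to agree that "delivery of intratumoral cisplatin is unlikely to adversely affect surgical feasibility".

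Two passages bear on when a DLT is decided. Section 4.2.2 says: "Primary endpoint adjudication for DLT will occur after the 2 week post-procedure evaluation and laboratory values are completed". Section 6.2.1.1 has the PI evaluate all adverse events when each patient's own study period ends, and counts any CTCAE event of grade 3 or higher as a DLT.

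**The concern.** The injection is given before surgery, and the synopsis postulates that it is a well-tolerated neoadjuvant therapy. Whether it makes the operation or the recovery harder is part of that question. The plan asks a surgeon to predict at entry that feasibility will not suffer. It then measures whether and when surgery happens, but not what happens during or after it. At stake is the secondary safety profile (6.2.2.1), which as written describes the pre-operative period only.

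The cut-off also ties each patient's recording period to the surgery date. Section 6.5.1 tabulates adverse events by dose tier and states no allowance for length of follow-up.

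**Working it through.** **Inputs.** Recording ends at the earlier of resection and day 30 (4.2.3, 7.2.8, 8.1.1.4). Surgery falls on days 14 to 30 (4.3.7). Adverse-event contacts are within 36 hours, on days 5 to 9 and on days 12 to 16 (4.3.3 to 4.3.5). The sample size is 10 to 12 (6.3).

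**The plan's own figure.** Six patients at each of two dose levels gives 6 × 2 = 12, as 6.3.2 states. The point below does not depend on it.

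**Recording window.** For surgery on day s, the window is min(s, 30) and the post-operative days captured are max(0, min(s, 30) − s). With recording to day 30 regardless of surgery, the post-operative days captured would be max(0, 30 − s).

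| Surgery day | Window now (days) | Post-operative days now | Post-operative days if recorded to day 30 |
|---|---|---|---|
| 14 | 14 | 0 | 16 |
| 21 | 21 | 0 | 9 |
| 28 | 28 | 0 | 2 |
| 30 | 30 | 0 | 0 |
| after 30 | 30, closed before the operation | 0 | 0 |

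The number of post-operative days is zero for every surgery date. The calendar window varies by a factor of 30/14 = 2.14; the shortest is 14/30 = 47% of the longest.

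**Active surveillance.** There are three scheduled adverse-event contacts, the last by day 16 at the latest. A patient resected after day 16 can have all three, whatever the surgery date. A patient resected on day 14 or 15 may not yet have had the third, which can be as late as day 16. Adverse-event recording could then close before the evaluation on which 4.2.2 bases DLT adjudication.

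**Intra-operative events.** Under 4.2.3 monitoring lasts *until* resection, which suggests that the operation is excluded. Under 7.2.8 recording ends *following* resection, which suggests that it is included. On the second reading, a grade 3 intra-operative event already meets the DLT definition in 6.2.1.1, which has no attribution condition.

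**What 10 to 12 patients could show.** The documents give no post-operative complication rate, so p is assumed. If all patients were resected and observed long enough, the chance of recording at least one event is 1 − (1 − p)^n:

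| Assumed p | n = 10 | n = 12 |
|---|---|---|
| 5% | 40% | 46% |
| 10% | 65% | 72% |
| 20% | 89% | 93% |
| 30% | 97% | 99% |

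For post-operative events the plan as written gives 0. These figures are ceilings for a day-30 cut-off, because late resections would have few post-operative days.

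**The case against.** The strongest objection is that extending recording without further change would disturb the primary endpoint. Under 6.2.1.1 a grade 3 surgical complication would count as a DLT whatever its cause. Resection can fall on days 14 to 16, inside the 2-week visit window, so such an event could precede adjudication even under 4.2.2. This stands, and it means that the DLT passages must be reconciled in the same amendment.

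A day-30 cut-off also gives unequal post-operative observation, from 16 days down to none, and the pre-resection period still varies. With 10 to 12 patients and no surgical control, post-operative events cannot be attributed to the injection. Separate tabulation makes that confounding visible but does not remove it. Both points stand as limits of the change. They are not reasons to keep no record.

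A reader might infer several stronger readings that the documents do not support.

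- *That about half of the adverse events are missed in early resections.* Under a constant hazard, a 20% risk by day 30 would appear as 1 − 0.8^(14/30) = 9.9% by day 14. Nothing in the documents supports a flat hazard after a single injection, and no adverse-event visit is scheduled after day 16 for anyone. The later days are largely passive follow-up, apart from the CT allowed on days 12 to 30.
- *That surgical impact is never assessed.* Delay and time to surgery are measured, and 7.1.5.1 treats unanticipated findings on the pre-resection CT as potential adverse events.
- *That almost every patient leaves follow-up early.* Section 4.3.7 allows for surgery not being planned, and no distribution of surgery dates is given.
- *That the comparison of dose tiers is biased.* Nothing in the documents links surgery date to dose. Chance imbalance is possible with so few patients, but no systematic direction follows.
- *That a specific operative harm is expected.* The fistula described in section 2.3 occurred with concomitant re-irradiation, and 3.2.4 excludes prior radiation to the study lesion.

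**Conclusion.** The point holds for post-operative harm. On the plan's own dates no post-operative day is recorded for any patient, and whether intra-operative events are recorded depends on which of two sections is followed. The safety profile in 6.2.2.1 therefore cannot describe peri-operative tolerability of the injection.

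The variation in the calendar window, 14 to 30 days, is real but secondary. The loss of active surveillance is much smaller than 47% suggests, and is confined to day 14 or 15 resections that precede the 2-week visit.

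The main effect is on a secondary endpoint. The primary objective, the MTD, is touched only through that early-resection case and the unreconciled DLT passages. The finding on post-operative days needs no assumption beyond the stated dates. The detection probabilities rest on assumed rates and complete resection. The change is worth making, but the dose escalation does not depend on it.

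**What to change.** 1. Reconcile *until* in 4.2.3 with *following* in 7.2.8.
2. Amend 4.2.3, 7.2.8 and 8.1.1.4 so that recording continues to 30 days after cisplatin for every patient, regardless of surgery. Take intra-operative and post-operative events from the surgical chart.
3. In 6.5.1, tabulate events on or after resection separately from earlier events. Keep that table descriptive, and show each patient's days of post-operative observation.
4. Reconcile 6.2.1.1 with 4.2.2, so that the added post-resection events do not change the DLT count.

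The cost is a few amended sentences and chart abstraction; section 7.2.4.1 already draws on clinic notes and other medical-record sources. No visit or procedure is added. There is some extra reporting work, because section 8 sends every SAE to the DSMC within 10 working days whatever its relatedness. Two limits remain: post-operative events are confounded by surgery, and patients resected near or after day 30 gain little or no post-operative observation.

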## 8. ADVERSE EVENT REPORTING:

Type of Event	To whom will it be reported	Time Frame for Reporting	How to report?
Death of a research subject unless the death is expected (e.g. due to disease progression).	UVMCC DSMC and UVM IRB	DSMC: Within 24 hours IRB: Within 24 hours of knowledge of the event	DSMC: Email IRB: RNI Click form
Serious Adverse Event (SAE), regardless of relatedness of expectedness	UVMCC DSMC. Per IRB policy, unexpected, related SAEs are reported	DSMC: Within 10 working days from the time the study team received knowledge of the event. IRB: 24 hours	DSMC: Email IRB: RNI Click form
Non-serious AEs	UVMCC DSMC and UVM IRB	At quarterly DSMCC report. Annually at IRB Continuing review.	DSMC: Email IRB: Click form

### 8.1. Unanticipated Problems and Protocol Deviations

8.1.1. Definition of an unanticipated problem:

8.1.1.1. An unanticipated problem is any event/experience that meets ALL 3 criteria below:

8.1.1.1.1. Unexpected (in terms of nature, severity, or frequency) given: (a) the research procedures that are described in the protocol-related documents, such as the IRB-approved research protocol and informed consent document; and (b) the characteristics of the subject population being studied;

8.1.1.1.2. Related or possibly related to a subject's participation in the research;

8.1.1.1.3. Suggests that the research places subjects or others at a greater risk

of harm (including physical, psychological, economic, or social harm) related to the research than was previously known or recognized.

8.1.1.2. Definition of a protocol deviation:

8.1.1.2.1. A protocol deviation is any variance from the protocol involving a subject or subjects that is not approved by the IRB prior to its initiation or implementation, and occurs when a member of the study team departs from the IRB-approved protocol in any way without the investigator first obtaining IRB approval

8.1.1.3. Recording/reporting of Unanticipated Problems and Protocol Deviations will begin after the subject signs consent

8.1.1.4. Recording/reporting of Unanticipated Problems and Protocol Deviations will end at surgical resection or 30 days after cisplatin delivery, whichever occurs first.

8.1.2. Unanticipated Problem, and Protocol Deviation reporting.

Type of Event	To whom will it be reported	Time Frame for Reporting	How to report?
Unanticipated Problems that are not AEs or protocol deviations.	IRB and DSMC	Within 7 days to both the IRB and DSMC	DSMC: Email IRB: Click form

## 9. DATA COLLECTIONS METHODS

9.1. Endpoints of the study are described in Section 6 of the protocol

9.2. Endpoints will be collected/recorded using protocol-specific Case Report Forms (CRFs), and source documents and captured in a REDCap database

9.3. The database is located on the secure UVM server and is firewall protected.

9.4. Correlative sub-studies, will link specimens other research data using the following:

9.4.1. All specimens (including CT scans) will be deidentified and scrubbed of HIPPA identifiers. A study number will be assigned. Only the PI and primary study coordinator will have access to the key to link study number with patient information.

9.5. The UVMCC DSM Report will be provided to the UVMCC

9.6. The UVMCC DSMC will be responsible for overseeing the study data

9.7. The PI will perform aggregate review of:

- 9.7.1. All AEs
- 9.7.2. Unanticipated Problems
- 9.7.3. Protocol violations
- 9.7.4. Audit results
- 9.7.5. Application of dose finding escalation/de-escalation rules
- 9.7.6. Application of study designed stopping/decision rules
- 9.7.7. Early withdrawals
- 9.7.8. Whether the study accrual pattern warrants continuation/action
- 9.7.9. Endpoint data

9.8. This aggregate review will occur quarterly

**1. TABLE OF STUDY VISITS AND PROCEDURES:**

	Screening	Phase 1: Intratumoral Cisplatin Protocol					
		Pre-Bronchoscopy	Bronchoscopic Procedure	24H Followup	1 Week Followup	2 Week Followup	Surgical Resection**
Study Visit							
Informed Consent	X						
History and Evaluation	X			X	X	X	
Research Biopsies			X				
Delivery of Cisplatin			X				
Cisplatin Blood Levels			X	X	X		
CXR	X (pre-bronchoscopy if no imaging within prior 7 days)		X (post-procedure)				
24H Post-Procedure Follow Up				X			
Hematology Panel	X				X	X	
Chemistry Panel	X				X	X	
Liver Panel	X				X	X	
Albumin	X						
Blood Draw for Research			X				X (day of resection)
Review of Adverse Events and Concomitant Medications				X	X	X	
Chest CT Scan (non-contrast if not performed or inadequate will be ordered for research purposes)	X					X	
Obtain Research Resected Pathology Specimen							X (fresh and fixed)

\* Research biopsies will be evaluated for changes in immunocellular infiltrate vs. resection specimen

\*\*Surgical resection to occur 14-30 days post-procedure

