6.2.2.1. Safety profile of intralesional cisplatin as classified by the CTCAE, v5.0

6.2.2.2. Proportion of cisplatin-treated subjects proceeding to surgery without extended local injection-related delay, defined as >30 days from preplanned surgery date (21 days from preplanned surgical date with 7-day window to allow for operating room [OR] scheduling)

6.2.2.3. Time to surgery from intralesional therapy.

6.2.3. **Biomarker and Surrogate Endpoints for Research Purposes:**

6.2.3.1. The below assays will be performed from:

6.2.3.1.1. Blood samples, pre-procedure on the date of the bronchoscopy and pre-procedure on the date of the surgical resection

6.2.3.1.2. Three (3) needle biopsies obtained at the time of bronchoscopy before cisplatin delivery

6.2.3.1.3. Seven (7) needle biopsies obtained from the ex-planted resection specimen (3 for platinated DNA, 1 for tumor organoid, 3 for other biomarker assessments described below)

6.2.3.1.4. Approximately 20 sections of fixed tissue from the resected tumor (final amount to be determined by pathology following obtaining all necessary tissue for clinical care, including any additional candidacy for clinical trials)

Objectives	Endpoints
Secondary To assess pathologic responses (PR) in the resected tumor following a single intra-tumoral administration of cisplatin in subjects with early stage NSCLC	

Proportion of cisplatin-treated subjects with major pathologic response (MPR), i.e., <math>\geq 90\%</math> reduction in viable tumor cells, at the time of NSCLC resection

Proportion of cisplatin-treated subjects with pathologic complete response (pCR), i.e., no residual viable tumor cells, at the time of NSCLC resection

Change from baseline in percent of residual viable tumor cells (% RVT) in cisplatin-treated subjects at the time of NSCLC resection

Exploratory To assess radiologic responses in the tumor following a single intra-tumoral administration of cisplatin in subjects with early stage NSCLC	

Tumor response rate evaluation (<math>\Delta</math> tumor size) according to RECIST 1.1 criteria

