To explore the change from pre-treatment baseline in measures of immune activation in the blood and tumor (eg, percentages of immune cell subsets, numbers of T-cell clones, concentrations of serum cytokine levels)	
Pre- and post-treatment in the bronchoscopic biopsy and surgically resected tumor samples, respectively:
 

Tissue levels of immune-related gene expression as measured by appropriate techniques such as RNA-sequencing in biopsy samples collected at diagnosis and time of resection

Tissue frequencies of immune cell subsets determined via semi-quantitative immunohistochemistry (IHC) analysis of diagnostic biopsy and surgically-resected tissue specimens

To assess changes in T cell clonality in blood by TCR-sequencing (via DNAseq) at baseline and after therapy, TCR repertoire sequencing will be performed on the tumor to profile in the blood

Tumor mutational burden will be assessed

Objectives	Endpoints
	
by next generation sequencing.
 
Pre- and post-treatment blood:
 
 
Changes in the concentrations of immune activation and inflammation markers in the serum before and after treatment. Serum cytokine and inflammatory biomarker (e.g., hs-CRP, IL-6, TNF-<math>\alpha</math>) concentrations will be measured by appropriate techniques such as Mesoscale Discovery (MSD).
 
Serum neutrophil-to-lymphocyte ratio (NLR): Defined as neutrophil count divided by lymphocyte count, as determined by complete blood count (CBC) with differential conducted at baseline and after treatment.
 
Change in frequencies of immune cell subsets in blood as measured by flow cytometry (eg, CD3, CD8, PD-1) at baseline and after treatment (absolute frequencies and percent change from baseline).
 
To assess changes in T cell clonality in blood by TCR-sequencing (via DNAseq) at baseline and after therapy. TCR repertoire sequencing will be performed on the biopsy sample of the tumor to ID clones specific to the tumor to profile in the blood.
 

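### Scheduled review of adverse events and concomitant medication stops at the 2-week visit, although AE recording runs to resection or day 30

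*Combined protocol and SAP*

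**What the plan says.** **Scheduled review.** The row "Review of Adverse Events and Concomitant Medications" in the Table of Study Visits and Procedures has marks under the 24-hour, 1-week and 2-week follow-ups only. The visit text agrees: the AE script is prescribed at those three contacts (4.3.3.1, 4.3.4.1, 4.3.5.1). The last has a window: "Participants will undergo an evaluation by a physician or advanced practice provider between 12-16 days post-procedure" (4.3.5.1).

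**AE window.** Section 4.2.3 states: "The patient will be monitored for adverse events until surgical resection or for 30 days after cisplatin delivery, whichever occurs first". Section 7.2.8 repeats the limit for recording: "Recording/reporting of AEs will end following surgical resection or 30 days after cisplatin delivery, whichever occurs first".

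**Surgery.** Section 4.3.7 states: "Surgical Resection, if planned, will be scheduled between 14 and 30 days after delivery of the cisplatin". The only study procedure listed beneath it is a blood sample: "Approximately 15mL of blood will be drawn for research purposes on the day of (prior to) the resection procedure" (4.3.7.1).

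**Use of that sample.** Section 6.2.3.1.1 names the biomarker draws as "Blood samples, pre-procedure on the date of the bronchoscopy and pre-procedure on the date of the surgical resection". The exploratory endpoints include "Changes in the concentrations of immune activation and inflammation markers in the serum before and after treatment", and also immune cell subsets in blood by flow cytometry.

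**The concern.** The schedule and the AE window end at different times. A site that follows the table asks its last AE and medication question on days 12-16, while recording may stay open to day 30. No section schedules such a question later, either at resection or at day 30 for a patient who is not resected.

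The length of the unasked interval is set by the surgery date, so ascertainment is uneven between patients. It is weakest in those with late or no surgery. That is an awkward group to question least, because delayed resection is itself to be reported as an AE (7.1, other potential risks) and injection-related delay is a secondary endpoint (6.2.2.2). The affected outputs are the safety profile (6.2.2.1) and the AE tables by dose tier (6.5.1). Several Appendix C items, such as ringing in the ears, tingling and altered taste, are symptoms that a patient may not mention unless asked.

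A second, smaller matter is the post-treatment immune sample. A drug taken at home between the 2-week visit and resection, such as a steroid or an antibiotic, has no scheduled record. With a single treated arm, its possible effect on serum cytokines or T-cell subsets could not be examined afterwards.

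**Working it through.** The plan gives no figure for this interval, so there is none to reproduce. The check is a difference in days.

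**Inputs**
- V, day of the last scheduled review: 12 to 16 (4.3.5.1; the table marks no later review).
- S, day AE recording ends: the day of resection, scheduled for 14 to 30 (4.3.7), or day 30 without resection (4.2.3, 7.2.8).
- Full window: 30 days.
- Planned patients: 10 to 12 (6.3.1, 6.3.2).

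**Formula.** Unasked interval = max(0, S - V). It is set to 0 when the visit falls on or after the day of surgery.

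| Last review (V) | S = 14 | S = 21 (illustrative) | S = 30 |
|---|---|---|---|
| Day 12 | 2 days | 9 days | 18 days |
| Day 14 | 0 days | 7 days | 16 days |
| Day 16 | 0 days | 5 days | 14 days |

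As a share of the 30-day window, the last column is 18/30 = 60%, 16/30 = 53% and 14/30 = 47%. The full range is 0 to 18 days.

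**Weight of one event.** With 10 to 12 patients, one patient with an unrecorded event shifts a crude proportion by 1/12 = 8% to 1/10 = 10%.

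**What remains after the 2-week visit**

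| Provision | Section | Asks the patient about symptoms or medication? |
|---|---|---|
| AE data taken from clinic notes, laboratory results and the EMR | 7.2.4.1 | No, record review |
| Chest CT on days 12-30, unanticipated findings assessed as potential AEs | 4.3.6, 7.1.5.1 | No, imaging |
| Investigator's evaluation of AEs at the end of the patient's study period | 6.2.1.1, 7.2.4.1 | Not specified as a patient contact |
| Research blood draw on the day of resection | 4.3.7.1 | Not specified, but the patient is present |

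**Primary endpoint.** Section 4.2.2 places DLT adjudication after the 2-week evaluation and laboratory results, and the scheduled reviews cover that period.

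**The case against.** The strongest reply is that the text already obliges the site to capture AEs to the end of the window (4.2.3, 7.2.8), so an empty cell in a table cancels nothing. Records, the CT and the end-of-period review all continue. Enrolled patients are expected to be surgical candidates (3.1.7), so many may have intervals well short of 18 days. A share of days is not a share of events missed, and the main decision, on DLT, is made at 2 weeks.

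Most of this stands, and it limits the weight of the point. It does not remove it: none of the continuing routes is specified as asking the patient anything, and the documents do not say how an obligation to day 30 is met after days 12-16.

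Four stronger readings may suggest themselves, and the documents do not support them.
- **No contact after the 2-week visit.** The research CT may fall later, and blood is drawn on the day of resection. What is missing is a scheduled AE or medication question.
- **No medication baseline.** The surgeon's eligibility review covers medications (3.1.7), the table marks history and evaluation at screening, and baseline AE recording starts at consent (7.2.7). The most one can say is that this review is not designated as the study's baseline medication record.
- **The neutrophil-to-lymphocyte ratio is affected in the same way.** It comes from a blood count with differential, and the scheduled post-treatment counts are at weeks 1 and 2, where medication review is marked.
- **Late AEs are under-counted.** The documents show that they may be, not that they are.

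**Conclusion.** The point holds as a mismatch between the visit schedule and the protocol's own AE window. Scheduled solicitation ends 0-2 days before the close of AE recording for surgery on day 14, and 14-18 days before it (47-60% of the window) when follow-up reaches day 30. Late AEs may therefore be under-counted in the secondary safety profile and the AE tables by dose tier, to an extent that varies with surgery date. Medication use just before the resection-day cytokine and flow cytometry sample has no scheduled record. That second part applies only to resected patients, since the others give no such sample.

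A reader might infer that dose finding is compromised. On the wording of 4.2.2 it is largely unaffected. One caveat is that 6.2.1.1 places AE evaluation at the end of the patient's study period and treats any grade 3 or higher event as a DLT, so a later event could bear on the primary endpoint under that wording. The two sections should be reconciled.

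The result assumes that sites follow the table and the visit text as written, and that surgery falls in the planned window. The distribution of surgery dates is not given, so the typical interval is unknown. Severity is minor to moderate.

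**What to change.** 1. In the Table of Study Visits and Procedures, mark "Review of Adverse Events and Concomitant Medications" in the Surgical Resection column, and add the same review under 4.3.7. Carry it out at the existing pre-resection research blood draw with the Appendix C script. That script is headed for the 1-week contact and has no medication question, so add one and generalise the heading.
2. For patients not resected by day 30, add one telephone review at day 30 with the same script.
3. Optionally, record the medication list already reviewed at screening (3.1.7) as the study's baseline.

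I would not ask for a repeat of the immune summaries without patients who took particular drugs. In 10 to 12 patients it would tell little, and it would need a time window that nobody has defined.

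The cost is one table mark, one script item, a short call for a few patients and possibly a few more reported AEs. Sample size and the escalation rules are unchanged.
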